Statistical Methods:	
All randomized participants will be evaluated for depression (MADRS), suicidality (C-SSRS), and other efficacy endpoints while on the study. Analyses will be conducted under ICH E9 (R1) guidelines. C-SSRS is a safety endpoint.
 
Change from baseline in MADRS total scores through study exit to compare treatments will be analyzed using Mixed Model Repeated Measures analysis (SAS PROC MIXED) with Last Observation Carried Forward (LOCF) containing sex, baseline use of mood stabilizers, baseline use of anti-psychotics, BPRS rating scale (none, any) and evidence of a suicidal event in their lifetime (none, any) as stratification factors in the analysis. Additional analyses will alternatively rely on multiple imputation to assess the impact of dropouts. The NRX-101 and lurasidone treatment groups will be compared using stratified and unstratified log rank tests, as well as a proportional hazard model for time to relapse.

Sample Size Calculation:	Participants will be randomized in a 1:1 ratio (NRX-101:lurasidone). With 37 participants per group, there is an 80 percent power to detect a mean 8.85-unit advantage for NRX-101 vs lurasidone for the CFB to Day 42, assuming a SD of 13.4 for NRX-101 versus lurasidone at 6 weeks for a two-sided hypothesis test with two-sided 5 percent Type I error. This equates to a 0.66 effect size.
Interim Analysis	
Two interim analyses are planned. The first interim analysis (IA) assessing safety will be conducted six weeks after the first 30-35 participants have been followed for 6 weeks and the second IA assessing futility (primary efficacy endpoint) will be performed after the first 45-50 participants have reached 42 days post-randomization.
 
Each interim analysis has a different objective with neither interim analysis spending any Type 1 error. The study will be stopped at the first interim analysis if Serious Adverse Events are deemed statistically significantly more common in the NRX-101 group compared to the lurasidone group in a manner deemed by the DMC to pose a potential danger to human subjects. The study will be stopped at the second IA for futility if the conditional power (CP) is less than 10%. In the event that the study is not stopped for either safety or futility, then enrollment will continue until a total of 74 subjects are randomized. This preserves two-sided <math>p=0.05</math> for the final analysis.

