## **12.7 Study Monitoring by the Drug Safety Monitoring Board (DSMB)**

The study will be monitored for safety, futility, and efficacy by a DSMB. Interim analysis for safety will be conducted six weeks after the first 30-35 participants complete Day 42 based on reported Adverse Events and Serious Adverse Events. The study may be stopped for safety concerns. A second DSMB assessment for safety and futility will be conducted when 45-50 participants have reached Day 42.

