### 18.4 Interim Analyses

Two interim analyses are planned. The first interim analysis (IA) assessing safety will be conducted six weeks after the first 30-35 participants have been followed for 6 weeks and the

second IA assessing futility (primary efficacy endpoint) will be performed after the first 45-50 participants have been followed for 6 weeks.

Each interim analysis has a different objective with neither interim analysis spending any Type 1 error. The study will be stopped at the first interim analysis if Serious Adverse Events are deemed statistically significantly more common in the NRX-101 group compared to the lurasidone group in a manner deemed by the DMC to pose a potential danger to human subjects. The study will be stopped at the second IA for futility if the conditional power (CP) is less than 10%. In the event that the study is not stopped for either safety or futility, then enrollment will continue until a total of 74 subjects are randomized. This preserves two-sided  $p=0.05$  for the final analysis.

The unblinded Sponsor biostatistician will perform the interim analyses for the Data Safety Monitoring Board (DSMB). The blinded Sponsor biostatistician will then adjudicate cases with respect to intercurrent events which impact analysis inclusion.

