### **19.3 Conventions**

Study visit dates will be analyzed using the nominal visit instead of the actual visit date.

Means, mean changes, standard deviations, and ranges will be presented separately for each treatment group. These endpoints will be evaluated using a paired t-test and between study treatment groups using an unpaired t-test at each time; these p-values will be presented as descriptive statistics.

For continuous variables, the mean, standard deviation, minimum, median and maximum will be presented, together with the total number of observations and the number of missing and non-missing values.

For ordinal and categorical variables, absolute and relative frequencies will be reported. Relative frequencies will be based on all observations and reported as percentages. Unless otherwise specified, percentages will be based on the number of participants with data and will not be calculated for missing categories.

Adverse events, medical histories, and concomitant medications will be reported on a patient and an event basis. Percentages will be calculated using the number of participants in the Safety population analysis set as the denominator.

All hypotheses will be tested at 5 percent (final analysis) level of significance using a two-sided test unless otherwise specified.

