## 20.5 Safety Endpoints

Adverse events will be classified by MedDRA. For each study treatment, safety data will be collected and analyzed while on treatment or until treatment-emergent adverse events are resolved. The type, incidence, timing (onset, duration), relationship, and severity of AEs will be reported for treatment-emergent and SAEs. Reasons for withdrawal due to AEs will also be reported. Narratives will be written for every AE classified as serious or associated with attempted suicide or death.

Safety and tolerability will be assessed using two-sided Fisher Exact tests to compare overall adverse event incidence for NRX-101 vs. lurasidone. Mean changes from randomization baseline will be displayed for each serum chemistry and hematology parameter as well as the shift; unpaired t-tests will be used to compare treatments. In addition, paired t-tests will be performed for the changes from randomization baseline for each study treatment group.

C-SSRS will also be considered as a safety endpoint but will be analyzed as a McNemar paired comparison test within treatment groups and as a Jonchkeere-Terpstra test to compare treatment groups.

Vital signs and ECGs (means and mean changes from baseline will also be evaluated within treatment groups using paired t-tests and between study treatment groups using unpaired t-tests. Percent with abnormal vital signs, heart rate, QRS duration, PR interval, RR interval, QT, and QTcF will be reported. McNemar paired comparison tests will be performed within study treatment groups for the abnormal discordant percent while two-sided Fisher Exact tests will be performed to compare incidences between treatment groups.

Blood draws for chemistries and hematologies will be evaluated within and between study treatment groups. Abnormality rates will be presented relative to established site-specific normal ranges and whether or not the abnormality is clinically significant. McNemar paired comparison tests will be performed within study treatment groups for the abnormal percents while two-sided Fisher Exact tests will be performed to compare incidences between treatment groups.

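### SAP 18.4 ties the first-interim safety stop to a statistically significant SAE excess, which 30-35 patients seldom show at low SAE rates; SAP 12.7 sets no such condition for the same interim

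*SAP*

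**What the plan says.** SAP 18.4 sets the first interim, on safety, to be "conducted six weeks after the first 30-35 participants have been followed for 6 weeks". The study will be stopped there if "Serious Adverse Events are deemed statistically significantly more common in the NRX-101 group compared to the lurasidone group". The same sentence attaches a second requirement, namely that the excess arises "in a manner deemed by the DMC to pose a potential danger to human subjects". If it is stopped for neither safety nor futility, enrolment continues to 74. Protocol 16.6.3 and the Study Design and Interim Analysis entries of both synopses carry the same rule.

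SAP 12.7, matched by Protocol 15.7, describes the same interim differently. The review is "based on reported Adverse Events and Serious Adverse Events", and "The study may be stopped for safety concerns". It mentions no statistical test.

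No section gives the test, sidedness or alpha for the interim SAE comparison, an expected SAE rate, or the operating characteristics of the rule. The nearest general conventions are in SAP 19.3 ("All hypotheses will be tested at 5 percent (final analysis) level of significance using a two-sided test unless otherwise specified") and SAP 20.5, which plans "two-sided Fisher Exact tests to compare overall adverse event incidence for NRX-101 vs. lurasidone".

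**The concern.** In 18.4 significance comes first, and the board's judgement is a further requirement on top of it. The judgement can narrow the trigger but cannot widen it. With 15-18 patients per arm, an imbalance that would worry any board can fall short of p<0.05. A board that follows 18.4 alone would then find that the stated trigger has not been met and that continued enrolment is the next step described. A board that follows 12.7 would have an open remit on the same data.

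Safety is the stated objective of this interim. The participants are outpatients with active suicidal ideation, and the SAEs include attempted suicide (SAP 12.2.6.2) and hospitalization for worsening psychiatric symptoms (SAP 12.2.4). The board should not have to choose between two descriptions of its own authority.

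**Working it through.** **The plan's own figures.** The only power stated on a comparable footing is for the MADRS: 80% for an effect size of 0.66 with 37 per arm. It reproduces. A noncentral t with 72 degrees of freedom gives 80.0%, and the smallest significant effect size is 1.9935 × √(2/37) = 0.463, against the stated 0.462. Nothing equivalent is given for the safety stop.

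**Inputs.**
- From the documents: 30-35 patients and 1:1 allocation.
- Assumed: arms that differ by at most one patient.
- Assumed: two-sided Fisher at 5%. These are the SAP's general conventions, but 19.3 labels its level for the final analysis and 20.5 concerns overall AE incidence.
- Assumed and varied: the SAE rates.

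**Step 1: what counts as significant.** For *a* patients with SAEs on NRX-101 and none on lurasidone in equal arms of *n*, the two-sided p is 2·C(n,a)/C(2n,a).
- 15/15, 4 vs 0: 2 × 1365/27405 = 0.100, not significant.
- 15/15, 5 vs 0: 2 × 3003/142506 = 0.042, significant.

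The smallest significant splits in equal arms of 15, 16 or 17, and at 18 NRX-101/17 lurasidone, are 5 vs 0, 7 vs 1 and 9 vs 2. When NRX-101 has one patient fewer, they fall to 4 vs 0, 6 vs 1 and 8 vs 2. At 17/18, for example, 4 vs 0 has probability C(17,4)/C(35,4) = 2380/52360 = 0.045. The mirror-image table has probability 3060/52360 = 0.058, which is more likely than the observed table, so the two-sided test does not add it.

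**Step 2: chance of reaching such a split.** With X the number on NRX-101, Y the number on lurasidone and c(y) the smallest significant count, sum P(Y=y) × P(X≥c(y)) over independent binomials.
- 15/15, 20% vs 5%: 0.4633 × 0.1642 + 0.3658 × 0.0181 + 0.1348 × 0.0008 = 0.083.
- 17 NRX-101/18 lurasidone, 20% vs 5%: 0.3972 × 0.4511 + 0.3763 × 0.1057 + 0.1683 × 0.0109 = 0.221.

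The same enumeration for all splits of 30-35 patients:

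| Assumed SAE rates, NRX-101 vs lurasidone | Equal arms, or one more on NRX-101 | One fewer on NRX-101 (15/16, 16/17, 17/18) |
|---|---|---|
| 8% vs 2% | 0.4-0.8% | 2-3% |
| 20% vs 5% | 8-14% | 18-22% |
| 40% vs 10% | 33-45% | 44-51% |
| 20% vs 10% (twofold) | 4-6% | 9-10% |

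**Step 3: dependence on the unnamed test.** At 20% vs 5%, a one-sided Fisher test at 5% gives 12-23%, a two-sided chi-square 19-26%, and a one-sided chi-square at 5% 35-42%.

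**Step 4: is it only the interim size?** No. With 37 per arm, two-sided Fisher gives 36% at 20% vs 5%. The normal formula needs 76 per arm for 80% power. No feasible timing of this interim would make significance a sensitive trigger at these rates.

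**The case against.** The best defence is that 18.4 says when the study will be stopped and does not say that it can be stopped only then. On that reading 18.4 is a mandatory trigger, 12.7 adds discretion, and the sentence on continued enrolment does not exclude a stop under 12.7. There are also other safeguards. SAEs go to the Medical Monitor within 24 business hours, patients at imminent risk of suicide are to be discontinued, and the board reviews safety again at 45-50 participants. Low power for SAEs is inherent in a trial of this size.

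Much of this stands. A reader might infer that no safety stop is possible without significance, or that a fourfold excess would go unacted on about nine times in ten. The documents support neither. Section 12.7 allows a stop on concern alone, and a fourfold ratio does not fix any probability until a lurasidone SAE rate and a test are assumed.

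The defence does not remove the problem. Even as a mandatory trigger, 18.4 adds a significance test to a board judgement that should suffice, and it never says that the 12.7 discretion is unaffected. The clause giving the SAP precedence over the protocol cannot settle the matter, because both texts are in the SAP. That low power is inherent is a reason not to make significance a condition.

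**Conclusion.** The point holds for the rule in SAP 18.4, Protocol 16.6.3 and the synopses, and not for every route to a safety stop. With 30-35 patients, a 20% vs 5% SAE excess would meet the significance condition in 8-14% of trials, or 18-22% if NRX-101 has one patient fewer. This rests on a two-sided Fisher test at 5% and on SAE rates that the documents do not give. Across lurasidone rates of 2-10%, a fourfold excess meets the condition in under 1% to 51% of trials, so at best it is missed about half the time. The further requirement of board judgement can only lower these figures for the 18.4 rule. They do not measure the chance of a safety stop under 12.7. Two sections of one SAP describe different triggers for one interim, and they should be reconciled.

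**What to change.** In SAP 18.4, Protocol 16.6.3 and both synopses, remove statistical significance as a condition of the first-interim safety stop. State that the decision rests on the DSMB's judgement of the reported AE and SAE data, in agreement with SAP 12.7 and Protocol 15.7. If a p-value is given to the board, label it as information only, name the test, sidedness and level, and tabulate its operating characteristics over a range of assumed SAE rates.

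The cost is wording in two documents. The rule becomes less mechanical, and the board may have a few more imbalances to discuss. Efficacy Type I error is not inflated, because stopping for harm cannot produce an efficacy claim.

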## **19. ANALYSIS CONVENTIONS**

### **19.1 Software**

All calculations will be performed using SAS statistical software, version 9.3 or later, and StatXact, version 10 or later.

### **19.2 Display Formats**

All efficacy and safety data will be displayed in tables and listings separately for each treatment group.

### **19.3 Conventions**

Study visit dates will be analyzed using the nominal visit instead of the actual visit date.

Means, mean changes, standard deviations, and ranges will be presented separately for each treatment group. These endpoints will be evaluated using a paired t-test and between study treatment groups using an unpaired t-test at each time; these p-values will be presented as descriptive statistics.

For continuous variables, the mean, standard deviation, minimum, median and maximum will be presented, together with the total number of observations and the number of missing and non-missing values.

For ordinal and categorical variables, absolute and relative frequencies will be reported. Relative frequencies will be based on all observations and reported as percentages. Unless otherwise specified, percentages will be based on the number of participants with data and will not be calculated for missing categories.

Adverse events, medical histories, and concomitant medications will be reported on a patient and an event basis. Percentages will be calculated using the number of participants in the Safety population analysis set as the denominator.

All hypotheses will be tested at 5 percent (final analysis) level of significance using a two-sided test unless otherwise specified.

#### 19.4 Estimand Structure

Analyses will be conducted in accordance with ICH E9 (R1) analysis principles as summarized below.

Primary scientific question of interest	The primary study hypothesis is that treatment with NRX-101 is superior to lurasidone in improving symptoms of depression as measured by the MADRS over 6 weeks of treatment. The null hypothesis for the primary endpoint is the mean change from baseline of MADRS-10 for NRX-101 is the same as lurasidone while the alternative hypothesis is that the mean change from baseline of MADRS-10 is larger than the mean change from baseline of MADRS-10 for lurasidone. Baseline is defined as MADRS-10 score at Visit 2 (randomization).
Target population	The mITT population will be the primary analysis population. The mITT population is defined through appropriate inclusion/exclusion criteria as specified in the protocol and blinded BDRM decisions.
Treatment of interest	NRX-101
Outcome Variables	MADRS-10 (and C-SSRS) will be recorded as audio files and reviewed by central master-raters with any non-congruent subject-visits from any site with >10% non-congruent scores sent to a qualified independent adjudicator to be considered as the subject-visit primary study endpoint.
Summary Measure	The contrast-estimated MADRS-10 Week 6 MMRM will use all post-randomization data with LOCF in the mITT population excluding all outcomes after BDRM-approved exclusions. The model will include treatment and the following four baseline covariates in addition to baseline MADRS-10: (1) sex, (2) mood stabilizer use, (3) anti-psychotic use, and (4) evidence of suicide event in their lifetime. The model will include treatment group, study visit, the interaction between study visit and treatment group, baseline MADRS-10, and the four baseline covariates as fixed effects. An unstructured error structure will be assumed.
Intercurrent Events	A BDRM will adjudicate all intercurrent events which may redact outcomes after disqualifying events; these intercurrent events may represent major protocol deviations.

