### 16.2 Primary Hypothesis

#### *MADRS*

The primary study hypothesis is that treatment with NRX-101 is superior to lurasidone in improving symptoms of depression as measured by the MADRS over 6 weeks of treatment. The primary study hypothesis is that treatment with NRX-101 is superior to lurasidone in improving symptoms of depression as measured by the MADRS over 6 weeks of treatment. The null hypothesis for the primary endpoint is the mean change from baseline of MADRS-10 for NRX-101 is the same as lurasidone. Baseline is defined as MADRS-10 score at study entry.

The null hypothesis is no difference in the mean change in the MADRS-10 score from baseline to Day 42/exit between both treatment groups, while the alternative hypothesis is that there is a larger mean improvement in the NRX-101 group than the lurasidone group. The study is to have 80% power to detect a 0.66 effect size post-randomization for a two-sided test with 5% Type 1 error using mixed model repeated measures (MMRM).

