## 20. STATISTICAL METHODOLOGY

### 20.1 General Methodology

The Mixed-Effect Model Repeated Measure (MMRM) will be the primary analysis for the primary efficacy endpoint (MADRS change from baseline); an unpaired t-test will be a secondary analysis. The proportional hazard model (PHREG) will be the primary analysis for time to event endpoints (time to remission, time to discontinuation); the unstratified log rank test will be a secondary analysis. The MMRM and PHREG models will all include treatment and the following four baseline covariates:

- sex
- mood stabilizer use
- anti-psychotic use
- evidence of suicide event in their lifetime.

All primary analyses will be in the mITT population as primary and repeated in the Per Protocol population if >5 percent are excluded.

All of the instruments used to measure SSIB or depression constitute serial continuous and ordinal outcomes that will be analyzed using MMRM with LOCF to account for missing data and early discontinuations. The models will include treatment group, study visit, the interaction between study visit and treatment group, the baseline level of the variable being analyzed, and the above four pre-defined baseline stratification factors as fixed effects. The primary endpoint change from baseline MADRS-10 will be analyzed using the MMRM model which will include baseline MADRS; treatment group; study visit; study visit\*treatment; sex, mood stabilizer use, anti-psychotic use, and evidence of suicide event in their lifetime as defined above. An unstructured error structure will be assumed.

SAS PROC MIXED will be used for continuous endpoints.

In addition, supportive analyses will be performed using multiple imputation which will be performed to address any missing data. The method of Little and Rubin will be used. The presentation of the results for the primary efficacy endpoints using the ITT population will be based on the observed data with multiple imputation for missing endpoint data using SAS PROC MI. Missing data will be imputed using MCMC imputation under the assumption of a missing at random using the mITT population. The SAS® procedure PROC MI will be used for the MCMC imputation of 25 complete data sets.

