### **20.3 Secondary Efficacy Endpoints**

All of the instruments used to measure SSIB or depression constitute serial continuous and ordinal outcomes that will be analyzed using MMRM with LOCF, which accounts for missing data and early discontinuations. Results will be presented separately for each treatment group.

The models will include treatment group, study visit, the interaction between study visit and treatment group, the randomization baseline of the variable being analyzed, and the four baseline stratification factors as fixed effects. The reason for missing data will be evaluated as a condition of MMRM analysis.

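### The primary Week 6 MADRS MMRM is fitted to LOCF-filled scores, and the SAP does not settle whether its target is Week 6 or Day 42/exit

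*SAP*

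**What the plan says.** SAP section 13 gives the SAP precedence over the protocol. In section 19.4 the summary measure is a Week 6 contrast, and the "MMRM will use all post-randomization data with LOCF in the mITT population excluding all outcomes after BDRM-approved exclusions". Section 20.1 says that all depression and suicidality instruments "will be analyzed using MMRM with LOCF to account for missing data and early discontinuations". Section 20.3 repeats this for the secondary endpoints, and the synopsis pairs MMRM with LOCF as well.

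The primary target is worded in two ways. The contrast in 19.4 is at Week 6, and the synopsis claims "80 percent power to detect a mean 8.85-unit advantage for NRX-101 vs lurasidone for the CFB to Day 42". But the null hypothesis in section 16.2 is "no difference in the mean change in the MADRS-10 score from baseline to Day 42/exit between both treatment groups", and the synopsis methods describe the change as running to study exit.

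On intercurrent events, 19.4 says only: "A BDRM will adjudicate all intercurrent events which may redact outcomes after disqualifying events". It names no strategy for treatment discontinuation or for the redacted outcomes.

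Section 20.1 adds supportive multiple imputation: "Missing data will be imputed using MCMC imputation under the assumption of a missing at random using the mITT population".

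**The concern.** An MMRM with an unstructured covariance can use incomplete records directly, and its results are valid if data are missing at random. Filling the gaps first removes that feature. A score from Day 7, 14 or 28 is counted as an observed Day 42 score, so the patient is assumed not to have changed after leaving. As written, an outcome redacted by the data review meeting would also be replaced by an earlier score.

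This is the only primary test, and it opens the testing hierarchy in SAP 18.3. Unequal dropout is foreseeable. One safety objective (SAP 7.4) is fewer NRX-101 discontinuations for lack of efficacy or worsening suicidality. Time to treatment failure (SAP 16.3) is planned around a hazard ratio of 0.421, with failure including exits for lack of efficacy and for treatment-related adverse events.

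**Working it through.** **Inputs from the documents.** 37 per arm, SD 13.4, difference 8.85, two-sided 5% (SAP synopsis and 18.2); illustrative mean changes -16 and -10 (18.2); post-baseline visits at Days 7, 14, 28 and 42 (SAP section 8, Table 1).

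**Assumptions**, because the documents give no dropout rate or response curve: dropout of 10% to 30% per arm; last scores spread evenly over Days 7, 14 and 28; exit unrelated to score. The share of the final change reached at Days 7/14/28 is 30/50/80% (curve A), 45/65/85% (curve B) or 70/90/100% (curve C).

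**1. The plan's figure.** 8.85/13.4 = 0.660. A two-sample t-test with 72 df has 80.0% power, and the smallest significant effect size is 0.463 (stated: 0.462). The 80% reproduces, provided all 74 contribute a Day 42 score.

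**2. What the filled model estimates.** With no gaps, an unstructured covariance and a visit-by-treatment term, the Week 6 contrast without covariates is the difference in filled Day 42 means. For an arm with true mean change m, dropout p and average share s reached at exit:

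LOCF mean = m x [1 - p x (1 - s)]

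For A, s = (30+50+80)/3 = 53.3%; for B, 65%; for C, 86.7%. So 1 - s is 0.467, 0.35 and 0.133.

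**3. True difference -6 (-16 vs -10), same curve in both arms.**

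| Dropout NRX-101 / lurasidone | Curve A | Curve B |
|---|---|---|
| 20% / 20% | -6 x 0.907 = -5.4 | -6 x 0.93 = -5.6 |
| 30% / 10% | -13.76 + 9.53 = -4.2 | -14.32 + 9.65 = -4.7 |
| 10% / 30% | -15.25 + 8.60 = -6.7 | -15.44 + 8.95 = -6.5 |

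**4. No true effect, same curve, 30% dropout in one arm and 10% in the other.** The false difference is 0.2 x (1 - s) x |m|. Its smallest value is 0.2 x 0.35 x 10 = 0.7 (curve B, both arms -10). Its largest is 0.2 x 0.467 x 16 = 1.5 (curve A, both arms -16). The standard error is 13.4 x sqrt(2/37) = 3.12, so a normal approximation gives two-sided rejection of about 5.6% and 7.7%. Simulation over two SD patterns and two correlation structures gave 5.5% to 8.4%. A separate simulation with 40/62/86% of the change at Days 7/14/28 and both arms at -16 gave 6.3% to 8.5%. With equal dropout and the same curve, rejection stayed near 5%.

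**5. Equal dropout of 30%, different curves (C for NRX-101, A for lurasidone).**
- True -6: -16 x 0.96 + 10 x 0.86 = -15.36 + 8.60 = -6.8, an overstatement.
- No effect, both -10: -9.6 + 8.6 = -1.0. Both -16: -15.36 + 13.76 = -1.6. Simulated rejection is about 6% to 8%.

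**6. Early-termination scores.** Protocol 9.1.3 asks leavers, if possible, to complete the Day 42/early-termination visit, which includes MADRS. If all attend midway between visits, the shares become 40/65/90% (A) and 55/75/92.5% (B). Then 1 - s falls from 0.467 to 0.35 and from 0.35 to 0.258, about a quarter less. The range in step 4 becomes 0.5 to 1.1 points.

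**7. The alternative.** In the separate simulation of step 4, with a true 8.85 and exit random or dependent on observed scores, the observed-data MMRM gave 8.8 to 9.0. LOCF gave 6.9 to 9.9 under 10%/30% imbalance. When exit depended on the unseen score (30%/10% dropout, same curve in both arms), the observed-data MMRM was off by 0.85 to 1.05 points and LOCF by 0.0 to 2.7. LOCF was the closer in 112 of 160 such scenarios.

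**The case against.** The best defence is that LOCF is biased only against a chosen target. If the target is the exit score, as section 16.2 can be read, LOCF estimates it by construction, and under LOCF the two labels give the same number. That is correct. It shows why the target must be stated; it does not show that Week 6, the time point of the contrast and the sample size, is well estimated.

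Second, a non-LOCF check is already planned: the synopsis offers multiple imputation to gauge the effect of dropouts, and 20.1 presents primary results with it. That is a real mitigation. But it is supportive, assumes missing at random and leaves the primary p-value on LOCF.

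Third, the error is modest in most scenarios, and LOCF is often the closer when exit depends on unseen scores. This stands. It limits the severity and shows that neither analysis is reliably closer in that case.

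A reader might infer more than the documents support:
- *LOCF always favours one arm, or equal dropout is harmless or merely conservative.* That needs the same proportional curve in both arms. The SAP hypothesises a Day 14 difference (7.2), so differing curves are plausible, and step 5 shows the result.
- *An early exit score will be analysed as Day 42.* Early termination and Day 42 share a schedule column and visits are nominal (19.3), but no rule says so. It would not alter the Week 6 contrast while LOCF stays.
- *The subgroup endpoint's Day 42/exit wording shows the primary target.* It concerns a different endpoint.

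**Conclusion.** The point holds and should be fixed; the primary test is not invalid as it stands. The governing text fits the primary and secondary MMRMs to LOCF-filled scores, leaves two wordings of the primary target unreconciled, and names no strategy for discontinuation or redaction. Against Week 6, bias arises when patients leave while scores are still changing.

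If both arms follow the same proportional curve, equal dropout shrinks a true effect, and Type I error rises only with unequal dropout or timing. If the curves differ, equal dropout can also overstate the effect or inflate Type I error. In the cases worked, a true -6 moved by up to about 1.8 points, and rejection under no effect ranged from about 5.5% to 8.4%. These figures rest on assumed dropout and curves, with last scores at scheduled visits. They do not bound the error, and they shrink if leavers attend the early-termination visit.

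**What to change.** 1. Delete LOCF from the MMRM wording in the SAP synopsis, 19.4, 20.1 and 20.3, and fit the models to observed scores.
2. State one primary target in the synopsis, 16.2 and 19.4; Week 6 fits the contrast and the sample size. Name the strategy for treatment discontinuation and for outcomes redacted by the data review meeting. No MADRS is scheduled after the exit visit, so the observed-data MMRM corresponds to a hypothetical strategy. If another is chosen, say how it will be estimated.
3. Once LOCF is removed, assign each early-termination score to the visit window in which it was taken.
4. Keep LOCF only as a labelled sensitivity analysis beside the multiple imputation.
5. Add one missing-not-at-random analysis in the 25 imputed data sets. Worsen NRX-101 leavers' scores by increasing amounts while lurasidone leavers stay at missing at random, or vary the arms separately, and report where the conclusion changes. Worsening both arms together could favour NRX-101 if lurasidone loses more patients.

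Separately, tidy Day 42/exit in the subgroup endpoint (synopsis, 11.3, 17.1.2).

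The cost is SAP wording, one mapping rule and one extra run, plus some precision. Power at 8.85 points would be roughly 70-77% with 15-25% dropout in both arms and about 65-70% with 30%. The 37 per arm carries no dropout allowance, and leavers are not replaced (protocol 9.1.3).
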